**2. ABSTRACT**

Active duty service members and veterans with combat-related posttraumatic stress disorder (PTSD) have a lower response rate to evidence-based cognitive behavioral PTSD treatments (e.g., Prolonged Exposure) than their civilian counterparts (Steenkemp et al, 2015). Stellate ganglion blocks are an emerging treatment that may hold promise as an adjunctive treatment for PTSD when combined with an evidence-based treatment such as Prolonged Exposure. To date, no study has examined the potential benefits of a stellate ganglion block over and above cognitive behavioral treatment alone. This open-label pilot study will examine the safety and effectiveness of combining Massed Prolonged Exposure with a stellate ganglion block. The study will recruit 12 active duty or retired service members (age 18 to 60 years) who meet DSM-5 diagnostic criteria for PTSD on the Clinician-Administered Posttraumatic Stress Scale-DSM-5 at the baseline assessment. Participants will receive ten sessions of Prolonged Exposure (90-minute sessions) over the course of two consecutive weeks. The stellate ganglion block will be administered between the 1st and 2nd Prolonged Exposure sessions. Participants will be asked to complete assessment measures during treatment and one- and three-months following the completion of treatment. This study will provide valuable information about a novel intervention, stellate ganglion block, that may enhance cognitive behavioral PTSD treatment outcomes in active duty and retired service members.

**3. OBJECTIVES/SPECIFIC AIMS/RESEARCH QUESTIONS.**

The primary research objective is to conduct a pilot study exploring the potential treatment effectiveness and safety of a stellate ganglion block combined with Massed Prolonged Exposure in reducing PTSD symptoms in active duty and retired service members ( $N=12$ ). The second objective of the pilot is to examine whether the combination of both treatments will reduce comorbid symptoms more than was found in a recently completed trial of Massed Prolonged Exposure in active duty service members (Foa et al, 2018).

**Aim:** To conduct a pilot study to evaluate the safety and effectiveness of a stellate ganglion block (with ropivacaine) combined with Massed Prolonged Exposure for the treatment of PTSD in active duty and retired military service members.

**Hypothesis 1:** More than 50% of the patients who receive the stellate ganglion block and Massed Prolonged Exposure will no longer meet the clinician-assessed PTSD diagnostic criteria on the CAP-5 at one-month and three-month follow-up.

**Hypothesis 2:** More than 50% of the patients who receive the stellate ganglion block and Massed Prolonged Exposure will have a 10 point or greater reduction in PTSD symptoms on the PCL-5 at one-month and three-month follow-up.

**Hypothesis 3:** The adverse events associated with the stellate ganglion block will be minimal and temporary.

**4. MILITARY RELEVANCE**

When left untreated, posttraumatic stress disorder (PTSD) can persist for decades and is associated with marked functional impairment including increased risk of depression, suicidality, substance abuse, relationship dysfunction, healthcare utilization, missed work days, and disability (Crum-Cianflone et al., 2016; Jacobsen et al., 2001; Lambert et al., 2012; Maynard et al., 2017; Stanley et al., 2019). Following almost two decades of combat deployments to Afghanistan, Iraq, and surrounding locations, PTSD poses a significant threat to the United States' military force strength and places additional strains on the Veterans Health Administration. Estimates of the numbers of service members and veterans returning from these deployments with PTSD are as high as 20% (range: 7-20%; Institute of Medicine, 2014; Richardson et al., 2010). Importantly, these estimates do not include service members who develop PTSD through sexual or physical assaults, motor vehicle accidents, and other non-combat related traumas. Given the costs associated with military training and the potential loss of knowledgeable and experienced service members, it is in the best interest of the military to provide opportunities for service members with PTSD to receive highly efficacious treatments that enable them to become fully fit for worldwide duty. Because those who cannot be treated into remission are at a significant risk for discharge from active duty, the provision of PTSD treatments that are both highly efficacious and accessible to active duty military personnel are urgently needed.

**5. BACKGROUND AND SIGNIFICANCE.**

Trauma-focused therapies such as Prolonged Exposure (PE) are effective in reducing PTSD symptoms below the diagnostic threshold in up to 80% of patients in *civilian* populations (Bisson et al., 2007; Institute of Medicine, 2008, 2014b; Resick et al., 2002), with treatment improvements lasting for years (Resick et al., 2012). However, the treatment of combat-related PTSD in active duty and veteran populations has been less successful with only 50% experiencing significant symptom reduction following treatment (Steenkamp et al., 2015). The need for treatments that produce higher response rates in active duty military is paramount.

In a seminal study, STRONG STAR (South Texas Research Organizational Network Guiding Studies on Trauma and Resilience) examined the effects of PE in 366 service members with combat-related PTSD (Foa et al., 2018). While PE is traditionally delivered in weekly sessions over the course of months, this format can pose unique obstacles to care for military patients. Therefore, in an effort to enhance treatment accessibility, the study team developed a Massed Prolonged Exposure protocol that compresses treatment into once daily treatment over a two-week period. The treatment efficacy of Massed Prolonged Exposure (ten 90-minute sessions in two weeks) was compared to spaced PE (ten 90-minute sessions in 10 weeks). Importantly, massed PE and spaced PE were equally efficacious with approximately 50% of patients experiencing reductions in their PTSD symptoms below diagnostic threshold. Additionally, massed PE had a lower drop out-rate from treatment (13.6% versus 24.8%, respectively) and fewer reported adverse effects. While the results of this study are promising, there is room for improvement.

Stellate ganglion blocks (SGBs) are an emerging treatment that may hold promise as an adjunctive treatment for PTSD when combined with an evidence-based treatment such as PE. SGBs are typically used for pain management (Gunduz & Kenis-Coskun, 2017). The use of SGB to treat PTSD was first reported by Lipov and colleagues (2008) as a means to block physiological stress response symptoms associated with PTSD. Since this report, case studies and small clinical trials have provided support for SGB's efficacy in treating PTSD in military populations. Reduction in PTSD symptoms has been reported within hours of the procedure, with researchers noting the largest reductions in symptoms of hyperarousal and avoidance (Lipov et al., 2012; Lynch et al., 2016). In a case series of 166 active duty patients, Mulvaney and colleagues (2014) found that the majority of patients experienced significant reductions in PTSD symptoms that remained 3 to 6 months following the procedure. On the other hand, a randomized clinical trial with active duty service members and veterans found no difference between those who received a SGB consisting of 5mL of 0.5% ropivacaine and those who received a sham injection in symptom reduction (Hanling et al., 2016). However, their sample size was small (*N* = 42), and the majority of participants were undergoing medical disability evaluation boards, leading researchers to suggest that larger trials with populations less susceptible to possible secondary gains need to be conducted (Hanling et al., 2016; Summers & Nevin, 2017). Furthermore, there was no control of prior or ongoing evidence-based behavioral therapy in this study. Thus, SGB may be an appropriate adjunct to increase efficacy of PTSD treatment. To date, no study has examined the potential benefits of combining SGB with an evidence-based behavioral treatment such as PE.

**6. RESEARCH DESIGN**

This is a small, open-label treatment study that tests the potential safety and treatment effectiveness of a stellate ganglion block combined with Massed Prolonged Exposure. Each of the 12 participants will receive ten 90-minute sessions of Massed Prolonged Exposure and an injection of a stellate ganglion block between the first and second PE sessions.

**7. RESEARCH PLAN**

**7.1 Selection of Subjects**

**7.1.1. Subject Population.**

The study sample will consent and screen up to 27 active duty and retired service members recruited in the community and through Brooke Army Medical Center (BAMC), JBSA-Fort Sam Houston, Texas to analyze data from at least 12.

**7.1.2. Source of Research Material.** All measures are being administered for research purposes. For a complete list of measures, see Section 7.3.

Source of Research Material	Clinical Purposes (Y/N)	Research Purposes (Y/N)
AHLTA Clinical Records	Yes	Yes

Clinician Rating Scales	No	Yes
Self-Report Questionnaires	No	Yes

### 7.1.3. Inclusion and Exclusion Criteria.

#### Inclusion Criteria

1. Active duty or retired military service member (age 18- 65 years) as assessed with the Demographics and Military Service Characteristics Form
2. PTSD diagnosis as assessed by Clinician-Administered Posttraumatic Stress Scale (CAPS-5)
3. Able to speak and read English (due to standardization of outcome measures)
4. Defense Enrollment Eligibility Reporting System (DEERS)-eligible to receive care at Brooke Army Medical Center for the stellate ganglion block.

#### Exclusion Criteria

1. Current suicidal ideation severe enough to warrant immediate intervention (as determined by the Depressive Symptoms Index – Suicidality Subscale and the Self-Injurious Thoughts and Behaviors Interview short form and corroborated by a clinical risk assessment by a credentialed provider).
2. Current manic episode or psychotic symptoms requiring immediate stabilization or hospitalization (as determined by the Mini International Neuropsychiatric Interview, 7.0 Psychosis and Mania modules and corroborated by clinical judgment).
3. Other psychiatric disorders severe enough to warrant designation as the primary disorder as determined by clinician judgment.
4. Symptoms of moderate to severe substance (to include alcohol) use warranting immediate intervention based on participant self-report on the Alcohol Use Disorders Identification Test, observation of participant behavior, and clinical judgment.
5. Pregnancy (i.e. positive pregnancy test at screening) or breastfeeding as determined by a positive urine pregnancy test or by a “yes” response on the Supplemental Health Questionnaire for SGB.
6. Current anticoagulant use as determined by a “yes” response on the Supplemental Health Questionnaire for SGB.
7. History of bleeding disorder as determined by a “yes” response on the Supplemental Health Questionnaire for SGB.
8. Infection or mass at injection site as determined by a “yes” response on the Supplemental Health Questionnaire for SGB.
9. Myocardial infarction within 6 months of procedure as determined by a “yes” response on the Supplemental Health Questionnaire for SGB.
10. Pathologic bradycardia or irregularities of heart rate or rhythm as determined by a “yes” response on the Supplemental Health Questionnaire for SGB.
11. Symptomatic hypotension as determined by a “yes” response on the Supplemental Health Questionnaire for SGB.
12. Phrenic or laryngeal nerve palsy as determined by a “yes” response on the Supplemental Health Questionnaire for SGB.
13. History of glaucoma as determined by a “yes” response on the Supplemental Health Questionnaire for SGB.
14. Uncontrolled seizure disorder as determined by a “yes” response on the Supplemental Health Questionnaire for SGB.
15. History of allergy to local anesthetics as determined by a “yes” response on the Supplemental Health Questionnaire for SGB.

### 7.1.4. Description of the Recruitment and Prescreening Process.

Participants will be continuously recruited through the community and Brooke Army Medical Center (BAMC), JBSA-Fort Sam Houston, Texas through provider referrals, recruitment events, flyers strategically placed at Fort Sam Houston, study information on the STRONG STAR website, and social media. Providers can give their patients contact information for the study staff so that interested individuals may contact STRONG STAR directly. Alternatively, providers can obtain consent to contact from their patients that allows the study staff to contact the potential participant directly. Medical records will not be reviewed for recruitment purposes. Instead, study participants will be provider-referred or self-identified.

Under an IRB-approved HIPAA Waiver of Authorization, study personnel will conduct a brief discussion by telephone where the basic study inclusion and exclusion criteria will be reviewed to help the individual determine if he or she meets the study criteria or has obvious exclusions from the study protocol so as to prevent individuals from making unnecessary travel for consent and more in-depth screening. This information will be entered into a secure database as a phone call to

a potential participant or a phone call from a potential participant: name, phone number, name of study the caller is interested in, referral date, referral source, potential eligibility status, reason if not eligible, and verbal permission to contact the caller in the future for other studies. We will also record the date and time of the call, outcome of the call, and any notes. Subjects who agree to study participation will sign a consent document before any further screening will take place. Any individually identifiable information and Protected Health Information (PHI) collected on individuals who do not consent to participation will not become part of the research data. If participants agree to participate in the research, the identifiable data collected will become part of the participants' research records and will be stored according to the research confidentiality plan.

Active duty or retired military service members who are not eligible or interested in other IRB-approved STRONG STAR protocols will be told about this study. If interested, a member of the research team will review eligibility with these potential participants over the phone. If the person believes they may qualify for the study, the participant will be scheduled for an appointment in which consent will be obtained, and if authorized, the first baseline assessment will be completed.

#### **7.1.5. Consent Process.**

During the consent appointment, potential participants will have the study explained to them in a private location in-person using a paper form at the UTHSCSA STRONG STAR offices located at [name] or online using an electronic consent (eConsent). The preferred method is to use the eConsent process. Potential participants will be provided a link to the informed consent document (ICD). The potential participant will be given a copy of the informed consent document (ICD) to read. After the potential participant has read the ICD, they will be given the opportunity to take the consent home to discuss the research with family and friends. The research team, including a research nurse, will be available to answer any questions about the research. Once the potential participant has reached a decision, a member of the study team will review the risks and benefits of the study and ensure the participant understands the research. The participant will sign the consent form either electronically or on a paper form. A copy of the signed ICD will be given to the participant. As described in the consent, participants on active duty will have the option of having their Command notified by the Research Staff to ensure active duty Service Members are afforded the time to participate in the study. Command agreement to allow for duty time to participate in this study is not a requirement for study participation. A member of the study team will document the informed consent process in the medical record of the participant. Baseline assessment will occur after consent.

#### **7.1.6. Subject Screening Procedures.**

Once the consent is signed, participants will then be asked to complete the baseline assessments. The initial consent and screening will require up to 4 hours. This will include the completion of the questionnaires and interviews outlined in the table in Section 7.3 below.

This study involves remote and/or virtual research interactions with participants by the research staff. Research activities will be audio-recorded by an independent device (separate from the conferencing platform, i.e. Zoom). Therefore, privacy and confidentiality is not guaranteed due to the nature of the electronic conferencing platforms that will be used.

A baseline assessment will then be scheduled to immediately follow consent. This may occur in-person using paper forms or the participant will be logged into the STRONG STAR eCAP online data capture system to complete self-report baseline questionnaires.

If the participant has been referred from another STRONG STAR study and already undergone baseline testing within the past 30 days, the participant will be asked as part of the consent process to use these assessments rather than repeating the assessment battery. If the participant is newly referred to this study, if it has been more than 30 days since baseline testing for another study, or the participant declines use of previously completed assessments, he or she will meet with an evaluator and complete the full baseline assessment per protocol.

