During the course of the assessment, if a participant’s symptom reports indicate that he or she is at high risk for suicidality according to the “STRONG STAR Suicide\_Risk\_Assessment\_and\_Risk-Crisis\_Management” SOP, risk management procedures outlined in this SOP will be followed. If the research team feels that hospitalization should be considered, the participant’s primary care provider or unit will be contacted to escort the individual to the ED. If a participant reports experiencing psychotic or mania symptoms, or reports dangerous amounts of alcohol and/or substance use, additional assessment by a licensed provider for consideration of referral for clinical care and for screening participants out of the study will be conducted. If a participant is determined to be ineligible for the study for any reason, a referral back to the referring provider or the patient’s primary care provider for clinical follow-up will be made.

Once it has been determined that individuals meet the inclusion and exclusion criteria, participants will work with the research staff to schedule treatment and, if requested, secure a release from duty from their command or work to participate in the two-week treatment. Massed PE will be conducted by doctoral-level therapists at the UTHSCSA STRONG STAR offices. Participants will meet with their providers for individual, 90-minute sessions. They will then be asked to complete out-of-session treatment assignments throughout the rest of the day. Between the individual therapy session and out-of-session treatment assignments, participants will engage in approximately four to six hours of treatment per day, Monday through Friday, for two weeks. The stellate ganglion block injection will be administered between the first and second massed PE session at the BAMC Pain Clinic by qualified medical personnel supervised by MAJ [name] [name]. The BAMC SOP for the placement of a stellate ganglion block will be followed. A research nurse will be in attendance during the procedure and will recover the participant for at least 1 hour following the procedure.

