During PE treatment, participants will complete interim assessments of their PTSD symptoms, mood symptoms, trauma-related cognitions, and suicidal ideation preceding sessions 6 and 10. This abbreviated assessment battery will include the PTSD Checklist for the DSM-5, Patient Health Questionnaire-9, Depressive Symptom Index – Suicidality Subscale, and Posttraumatic Cognitions Inventory and should take less than 15 minutes to complete. The full assessment battery outlined in the measure section will be re-administered one- and three-months following the completion of treatment by an independent evaluator. These assessments may occur in person at the UTHSCSA STRONG STAR offices or online/by phone as needed to accommodate participant scheduling and circumstances.

In order to examine the safety of the stellate ganglion block in combination with massed PE for the treatment of PTSD, adverse event monitoring will be conducted throughout the treatment phase, at each interim assessment, and again at the one-month posttreatment and three-month follow-up assessments. STRONG STAR has well established standard operating procedures for adverse event monitoring. An adverse event that leads to hospitalization will be considered a serious adverse event (SAE), and adverse events that are unexpected and increase risk to participants will be considered an Unanticipated Problems Involving Risk to Subjects or Others (UPIRSO). SAEs and UPIRSOs will be promptly reported to the IRB. The categorization and relatedness of each potential adverse event will be adjudicated by the study team during weekly calls.

Study Procedures	Base Line	PE Day 1	SGB Txt between Txt PE Days 1& 2	PE Days 2-5	Interim Assess Day 6	PE Days 6-9	Interim Assess Day 10	PE Day 10	1wk Post txt	3wk Post txt	1M F/U	7wk Post txt	3M F/U
Phone Discussion													
Informed Consent	R												

Study Procedures	Base Line	PE Day 1	SGB Txt between Txt PE Days 1& 2	PE Days 2-5	Interim Assess Day 6	PE Days 6-9	Interim Assess Day 10	PE Day 10	1wk Post txt	3wk Post txt	1M F/U	7wk Post txt	3M F/U
Demographics and Military Service Characteristics Form	S,R												
Life Events Checklist for the DSM-5	S,R										R		R
Deployment Risk and Resilience Inventory-2	S,R												
Mini International Neuropsychiatric Interview (MINI 7.0) Psychosis and Mania modules	S												
Health Questionnaire	R										R		R
Health Questionnaire-Supplemental for SGB	S												

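### The only pre-treatment PCL-5 can be 30 days old at consent, with no cap on the further wait, so change before session 1 counts in the Hypothesis 2 response

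*Combined protocol and SAP*

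**What the plan says.** **Reuse.** Section 7.1.6 covers people referred from another STRONG STAR study who have "already undergone baseline testing within the past 30 days". At consent they are invited to let those earlier results stand in place of a new battery. A full new baseline is needed for new referrals, "if it has been more than 30 days since baseline testing for another study, or the participant declines use of previously completed assessments". The exemption covers the whole battery, so it includes the PCL-5 and the CAPS-5.

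**Wait to treatment.** Section 7.3 (Study Procedures) says that once eligibility is settled, "participants will work with the research staff to schedule treatment and, if requested, secure a release from duty". No maximum interval to PE session 1 is given there or elsewhere.

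**PCL-5 schedule.** The Section 7.3 table has a PCL-5 at baseline and then at the interim assessment before session 6. There is none on PE Day 1 or at the block visit.

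**Endpoint.** Hypothesis 2 (Section 3) is that more than half of patients "will have a 10 point or greater reduction in PTSD symptoms on the PCL-5 at one-month and three-month follow-up". It does not name the score from which the reduction is measured. Section 7.4.3 lists baseline, one month and three months as the assessment points, plans proportions with 95% confidence limits, and makes estimating the size of effect for a larger trial one of the pilot's goals. Section 7.4.2 also makes CAPS-5 severity a primary outcome.

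**The concern.** A change score in an uncontrolled study is only as good as its starting point. Here the start of measurement and the start of treatment can be weeks apart, and nothing is measured in between. Spontaneous improvement or deterioration, or other care received in that gap, becomes part of the apparent effect of the block plus PE.

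Two results are exposed: the proportion with a 10-point PCL-5 reduction, which is judged against 50%, and the effect size taken into planning of the larger trial. Change in CAPS-5 severity has the same weakness, because its baseline can be reused in the same way.

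**Working it through.** **1. Which score is the reference?** Hypothesis 2 does not say. Baseline is the only PCL-5 taken before treatment, and Section 7.4.3 names baseline as the first assessment point. That the reduction is measured from baseline is therefore an inference, but no other pre-treatment score exists.

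**2. How old can that score be?** The 30-day limit applies at consent. The wait from consent to session 1, *w*, has no limit. Treatment takes two weeks (12 days from first to last weekday) and up to three weeks (21 days) is allowed (Section 7.3).

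- Age of a reused baseline at session 1: 30 + *w* days.
- Baseline to the one-month visit: 30 + *w* + (12 to 21) + 30. With *w* = 0 this is 72 to 81 days, of which 30 precede treatment. With an assumed *w* = 30 it is 102 to 111 days, of which 60 precede treatment.
- Recall outside treatment is two weeks (Section 14, PCL-5), so a score taken 30 days before consent describes roughly days 44 to 30 before consent.
- For a fresh baseline the age at session 1 is *w* days, also uncapped.

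**3. Does anything else fill the gap?** Section 7.1.4 speaks of a first baseline assessment, but no second is described. Section 8.1 mentions weekly self-report measures, but the schedule puts none between baseline and session 1. The recruitment pace of two per month and the 12-month timeline in Section 12.0 describe the study as a whole and do not limit any participant's wait.

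**4. Illustration of size.** The plan has no figure of its own to reproduce: Section 7.4.1 states that no power analysis was done, and no SD or drift is given. Assumptions, none from the documents: change is normal with SD 8 to 12 points, *d* is the mean pre-treatment fall, and there is no treatment effect.

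P(drop ≥ 10) = 1 − Φ((10 − *d*)/SD)

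| SD | *d* = 0 | *d* = 3 | *d* = 5 | Increase over *d* = 0 |
|---|---|---|---|---|
| 8 | 1 − Φ(1.250) = 10.6% | 1 − Φ(0.875) = 19.1% | 1 − Φ(0.625) = 26.6% | 8.5 and 16.0 points |
| 12 | 1 − Φ(0.833) = 20.2% | 1 − Φ(0.583) = 28.0% | 1 − Φ(0.417) = 33.8% | 7.8 and 13.6 points |

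Only the last column belongs to this issue. The *d* = 0 column is ordinary variability that any baseline would carry.

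**5. The other direction.** With worsening of 3 or 5 points (*d* = −3, −5), SD 8 gives 1 − Φ(1.625) = 5.2% and 1 − Φ(1.875) = 3.0%. SD 12 gives 1 − Φ(1.083) = 13.9% and 1 − Φ(1.250) = 10.6%. These are about 5 to 10 points below the *d* = 0 values.

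**6. Dependence on the true effect.** With a true treatment change *t*, the numerator becomes 10 − *t* − *d*. At an assumed *t* = 20, a fall of 3 to 5 points adds about 5 to 10 points (SD 8: 89.4% to 94.8% and 97.0%; SD 12: 79.8% to 86.1% and 89.4%). At an assumed *t* = 8, just below the threshold, a 3-point fall moves the response rate from 40.1% to 55.0% (SD 8) or from 43.4% to 53.3% (SD 12). If all 12 participants shared that fall, the chance of at least 7 of 12 responders would go from 0.16–0.23 to 0.48–0.53.

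**The case against.** **Frequency is unknown.** Section 7.1.4 says that people "who are not eligible or interested in other IRB-approved STRONG STAR protocols will be told about this study", and a reader might infer that reuse will be common. The documents do not support that. Many such people may never have completed another study's baseline, the same section names several other recruitment routes, and reuse also needs testing within 30 days and the participant's agreement. If 3 of 12 were affected (an assumption), 8 to 16 points each is 3 × 0.08 to 3 × 0.16, about 0.2 to 0.5 of a participant. This stands as to reuse. The uncapped wait applies to everyone.

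**Direction is not established.** A reader might infer that the response rate must be inflated, for instance by regression to the mean. Entry is selected on the CAPS-5 diagnosis; the PCL-5 has no entry threshold, so regression on it is indirect. Regression from measurement error would also follow a fresh baseline. Section 4 describes untreated PTSD as able to last for decades, which lends no support to a fall within weeks. This stands: the bias can go either way.

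**Eligibility.** A reader might infer that exclusions for current conditions would rest on the old record alone. Section 7.1.3 requires a clinical risk assessment to corroborate the suicidality exclusion and clinical judgment for mania, psychosis and substance use. The block-specific health questionnaire was written for this study (Section 14), so another study's battery is unlikely to contain it. That inference fails.

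**It is a small descriptive pilot.** Even 7 of 12 has an exact 95% interval of 28% to 85%, so sampling error is large. In addition, Hypothesis 1 does not use the PCL-5. Both are true, but a wide interval does not correct a shifted reference, and the point estimate is meant to inform the next trial.

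**Conclusion.** The point holds as a gap in the definition of the starting score. On the text, the PCL-5 reference can be 30 days old at consent plus an unlimited wait, no score marks the start of treatment, and a single arm cannot separate what happens in that gap from treatment effect. The CAPS-5 severity baseline is equally exposed.

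The size is illustrative only: about 8 to 16 percentage points per affected participant, given an assumed SD of 8 to 12, no treatment effect and a 3 to 5 point fall. It would have the opposite sign under worsening. The documents do not support a count of affected participants out of 12, because that would require every participant to share a drift that the plan does not give. The study can run as designed, but its PCL-5 response rate should have a defined starting point, and the remedy is cheap enough to be worth making.

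**What to change.** 1. Add the existing short battery (PCL-5, PHQ-9, DSI-SS, PTCI) immediately before PE session 1. State that this PCL-5 uses the two-week recall that applies at follow-up; Section 14 sets one-week recall during treatment, so without this sentence the reference and the outcome could cover different periods.
2. Name that PCL-5 in Hypothesis 2 and Section 7.4.3 as the score from which the 10-point reduction is measured. Keep the screening or reused PCL-5 as a sensitivity baseline.
3. Report the interval from baseline to session 1 for every participant, and whether the baseline was reused.
4. Show change in CAPS-5 severity with and without participants whose CAPS-5 baseline was reused. The 30-day reuse of the interview can then stay.

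Cost: one schedule column, a few sentences, and a self-report battery that by the protocol's own estimate "should take less than 15 minutes to complete". The added participant burden is the only real downside. Change during treatment and follow-up remains uncontrolled, as in any single-arm study; this change only removes the pre-treatment part from the PCL-5 result.
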